Rigorous, randomized, placebo-controlled trials are necessary to determine whether lowdose testosterone augmentation will be an effective treatment for depression in women with inadequate response to antidepressant **therapy**. In this application, a double-blind, placebocontrolled trial of adjunctive low-dose testosterone for inadequate response to antidepressant **therapy** among MDD women is proposed.

*Specific Aim 1*. Low-dose testosterone augmentation improves depressive symptoms in women with MDD and partial/nonresponse to antidepressant therapy.

*Aim 1A.* We will investigate in female antidepressant therapy partial/nonresponders whether low-dose testosterone augmentation for 8 weeks leads to a significantly greater reduction in depressive symptoms than placebo.

*Aim 1B.* We will investigate whether a key mechanism underlying the effects of testosterone administration on depressive symptoms is an increase in neuroactive testosterone metabolites, including 3alpha-diol.

*Specific Aim 2.* Adjunctive low-dose testosterone is safe and well-tolerated in women with MDD and partial/nonresponse to antidepressant therapy. We will investigate whether low-dose testosterone augmentation therapy for 8 weeks is safe and well-tolerated in female antidepressant therapy partial/non-responders compared to placebo.

*Specific Aim 3.* Low-dose testosterone augmentation improves two specific RDoC construct symptoms (in the Arousal/Physiologic Processes Domain) in women: fatigue and sexual dysfunction. We will investigate in female antidepressant therapy partial/nonresponders whether low-dose testosterone augmentation for 8 weeks improves associated fatigue and sexual dysfunction compared to placebo.

*Specific Aim 4.* Low-dose testosterone therapy in women with treatment resistant depression will cause functional changes in the brain. We will investigate the mechanisms and functional neuroanatomy of the effects of testosterone on different regions of the brain in women with treatment resistant depression. This will serve as preliminary data for future studies and grants.

*Exploratory Aim:* We will investigate androgen and other hormonal correlates of functional and structural neuroanatomy in women with treatment resistant depression compared with healthy, non-depressed controls. This will serve as preliminary data for future studies.

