**Drug Safety:** We will measure free testosterone levels every two weeks and decrease the dose to 5 mg (0.5 ml) in any subject with a free testosterone level of more than 2x the upper limit of normal for females at one visit or 1.5x the upper limit of normal at two visits. If the free testosterone level remains above the same limits listed above after the initial dose decrease, the dose will be decreased to 2.5mg (0.25ml). In order to ensure success at raising levels during the

Form 2005

trial, dose increases by 5 mg increments (0.5 ml) daily will be made in subjects in whom the free testosterone level is less than the mean for age at any visit.

**Safety**: Patients will be carefully monitored by clinicians for side effects and potential toxicities with hirsutism and skin assessments. The blood draws will be performed by trained staff who have certificates documenting their ability to draw blood. We are performing a physical examination and routine laboratory tests prior to allowing anyone to enter the randomized phase of the protocol to ensure that subjects are medically stable. Close monitoring of patients throughout the study will ensure that adverse effects from treatment, exacerbation of symptoms, or emergence of suicidality, mania or psychosis will be promptly recognized so that patients can be treated appropriately following study discontinuation. All patients will be instructed on how to contact study clinicians in the case of an emergency. They will also be instructed on how to contact the Acute Psychiatry Service (APS) at MGH and the Patient Assessment Services (PAS) at Butler Hospital, which provide emergent psychiatric care on a 24h/day basis.

Every effort will be made to keep patients in the study. Acceptable reasons for early discontinuation include: 1) request of patient, 2) decision of physician, 3) serious adverse event, 4) worsening of depression requiring hospitalization, 5) emergence of hypomania, mania or psychotic symptoms, 6) pregnancy.

A Data Safety Monitor will review safety data, including adverse events and free testosterone levels twice-a-year and will be available in the interim to consider any urgent matters.

Partners Human Subjects Research Application Version Date: June 1,

Form 2005

Close skin contact with the area of application within an hour of application by a partner or child should be avoided.

AndroFeme contains almond oil. Therefore, individuals with almond allergies may be allergic to this preparation.

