Testosterone Antidepressant Augmentation in Women

NCT01783574

Version Date: February 1, 2017

Study Endpoints and Data Analysis

Specific Aim 1: We will investigate in women with partial/nonresponse to antidepressant therapy whether low-dose testosterone augmentation leads to a significantly greater reduction in depressive symptoms compared to a placebo group over an 8-week period.

Experimental Strategy and Endpoints: To investigate the effects of physiologic testosterone augmentation on antidepressant therapy partial/nonresponse, 50 women with partial/nonresponse to antidepressant therapy randomized to testosterone augmentation and 50 to placebo in the 8-week randomized, double-blind placebo controlled study delineated in the "Overall Protocol", will be compared. Depressive symptom endpoints will be measured at baseline and weeks 2, 4, 6 and 8. The primary endpoint will be MADRS score in weeks 2-8.

• These data will determine the effects of low-dose testosterone augmentation on depressive symptoms in women with partial/nonresponse to antidepressant therapy.

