Data Analysis: For Aim 1, the data will be analyzed using a mixed-effect linear regression model. The randomization will be stratified by site, estrogen use, and one vs. more than one adequate antidepressant therapy trial. The model will specify a baseline MADRS score and baseline non-responder vs. partial responder as covariates and then an "on treatment score," which is the score from weeks 2 through 8. The following will be entered into the model as covariates: baseline non-responder vs. partial responder, one vs. more than one adequate antidepressant therapy trial, baseline free testosterone level, baseline age and site (MGH or Butler Hospital). The on treatment score will have a fixed treatment effect and a random patient effect. We will examine interactions between menopausal status and effect to determine whether menopausal status moderates the treatment effect. This model is the same as in a repeated measures analysis of (co)variance with the assumption of compound symmetry. Our pilot data shown in Figure 2 fits this model. Specifically, based on our preliminary data, we expect a rapid improvement in depression severity by 2 weeks followed by maintenance of the effect of the subsequent 6 weeks. One advantage of this method is that it allows us to use data from patients who drop out early despite our plans to obtain follow-up data on all patients randomized and analyze all data obtained. A subject who drops out in the middle of the study will add data to the analysis. The drop-out rate should be low due to the relatively short duration of the study and the anticipated low side effect profile, the latter as confirmed in our pilot study in this population in which we had no drop-outs over the 8-week period. This model assumes that the drop-outs are missing at random. We will attempt to obtain 8-week observations on all patients, including drop-outs. Sensitivity analysis will be performed to determine whether our conclusions are sensitive to this assumption (185). Secondary analyses will determine whether the response of depressive symptoms to testosterone is affected by baseline androgens and neuroactive metabolites (including free testosterone level, DHEAS, and 3α -diol), estradiol, blood cortisol, late night cortisol and 8 a.m. salivary cortisol, and changes in the same variables over the 8-week period. Pre-treatment free testosterone level will be entered into the model as a covariate along with a treatment baseline interaction. Other covariates that will be explored will be age, menopausal status, baseline MADRS score, change in estradiol levels, change in free testosterone levels and BMI. As a secondary

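### The Aim 1 primary model lists no visit or arm-by-visit term, so drift in scores combined with unequal drop-out would bias the arm estimate, and the assumed flat effect cannot be checked

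*SAP*

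**What the plan says.** The SAP, Specific Aim 1, sets the endpoint: "The primary endpoint will be MADRS score in weeks 2-8". On timing it says: "Depressive symptom endpoints will be measured at baseline and weeks 2, 4, 6 and 8".

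The Data Analysis paragraph gives the model: "The on treatment score will have a fixed treatment effect and a random patient effect". The listed covariates are baseline MADRS, non-responder vs partial responder, number of adequate antidepressant trials, baseline free testosterone, age and site. Week or visit is not among them, alone or crossed with arm. The same paragraph equates the model with a repeated-measures analysis of (co)variance under compound symmetry. Such an analysis often carries a time factor, so the visit main effect is unclear rather than expressly excluded.

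The reason given for a single effect is pilot experience: "we expect a rapid improvement in depression severity by 2 weeks followed by maintenance of the effect of the subsequent 6 weeks".

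The paragraph lists the use of partial data from drop-outs as an advantage, assumes missingness at random, plans a sensitivity analysis of that assumption, and says the team will try to obtain week-8 observations on everyone. Week 8 by itself appears only as an exploratory remission rate.

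The Protocol's Drug Safety paragraph allows dose changes during the same weeks: "dose increases by 5 mg increments (0.5 ml) daily will be made in subjects in whom the free testosterone level is less than the mean". The mean in question is age-specific, and decreases are allowed when levels are high. Free testosterone is measured at weeks 2, 4, 6 and 8, which are also the MADRS visits.

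The SAP applies the same methods to SF-36 (under Aim 1) and to BFI, the primary endpoint of Aim 3.

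**The concern.** A model without visit treats all on-treatment scores of a patient as having the same expected value. If scores fall over weeks 2-8 in both arms, a woman who leaves early contributes only her early, higher scores. The arm that loses more women then looks worse even with no treatment effect. Missing at random does not protect against this, because the fault is a mis-specified mean. The direction depends on which arm loses more women.

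Second, a single treatment effect gives no view of how the arm difference evolves. The SAP expects it to be flat from week 2. Dose may change in either direction at the visits where MADRS is scored, so flatness is an assumption that should be checked. The Protocol's Background section says that this approach has not been studied in a double-blind randomised trial, so the pilot cannot show the time course of a testosterone-placebo difference.

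**Working it through.** **Inputs from the documents.** Four post-baseline scores (weeks 2, 4, 6, 8); 50 women per arm; a random patient effect with compound symmetry. The documents give no SD, within-patient correlation, drift or planned drop-out rate; the pilot had no drop-outs. There is no figure in the plan to reproduce.

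**Assumptions.** Between-patient SD 6 and residual SD 4 (variances 36 and 16). No treatment effect. Scores fall by d points per visit in both arms. Half of drop-outs leave after week 2 and half after week 4, regardless of their scores. Baseline covariates are ignored.

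**Step 1: complete data.** All women have four scores and equal weight. A common drift adds -1.5d to each arm mean and cancels. The standard error is sqrt(2/50 × (36 + 16/4)) = sqrt(1.6) = 1.26. A separate simulation (50 per arm, SD 8, correlation 0.6, a fall of 6 points from week 2 to week 8, 400 runs) gave the same estimate (0.048) and standard error (1.335) with and without visit.

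**Step 2: unequal drop-out, visit omitted.** A woman with k scores has weight w(k) = k/(16 + 36k):

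- w(1) = 1/52 = 0.01923
- w(2) = 2/88 = 0.02273
- w(3) = 3/124 = 0.02419
- w(4) = 4/160 = 0.02500

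Her mean fall is 1.5d if she completes, 0 if she leaves after week 2, and 0.5d if she leaves after week 4.

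- 5% drop-out: (0.95 × 0.02500 × 1.5 + 0.025 × 0.02273 × 0.5) / (0.95 × 0.02500 + 0.025 × 0.02273 + 0.025 × 0.01923) = 0.035909/0.024799 = 1.448, so the arm shows a fall of 1.448d.
- 25% drop-out: (0.75 × 0.02500 × 1.5 + 0.125 × 0.02273 × 0.5) / (0.75 × 0.02500 + 0.125 × 0.02273 + 0.125 × 0.01923) = 0.029545/0.023995 = 1.231, a fall of 1.231d.

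The spurious arm difference is (1.448 - 1.231)d = 0.217d. The standard error is sqrt(1/(50 × 0.024799) + 1/(50 × 0.023995)) = 1.28.

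**Step 3: the planned week-8 recovery.** A woman who leaves after week 2 but gives a week-8 score has mean fall (0 + 3)d/2 = 1.5d with weight w(2). One who leaves after week 4 has (0 + 1 + 3)d/3 = 1.33d with weight w(3). Repeating Step 2:

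| Drop-out | Week-8 score obtained from drop-outs | d = 1 | d = 2 | d = 3 |
|---|---|---|---|---|
| 5% vs 25% | none | 0.22 | 0.43 | 0.65 |
| 5% vs 25% | half | 0.12 | 0.23 | 0.35 |
| 5% vs 25% | all | 0.02 | 0.03 | 0.05 |
| 10% vs 20% | none | 0.11 | 0.22 | 0.32 |

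These use known variances. When the variances are estimated, the residual absorbs some of the drift and the shift is slightly smaller: simulation gave 0.22, 0.41 and 0.57 for the first row. With visit in the model there was almost no shift.

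**Step 4: what a constant effect can hide.** With complete data the single effect equals the mean of the four visit effects. If the effect is flat from week 2, that is 100% of the week-8 effect. If 25/50/75/100% of it were present at the four visits, the average would be 62.5% of the week-8 effect; for 50/75/100/100% it would be 81%. These profiles are illustrations only.

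**Step 5: cost in precision of week 8 alone.** With complete data its standard error is sqrt(2/50 × (36 + 16)) = 1.44, against 1.26 for the average.

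**The case against.** A reader might infer that the primary endpoint contradicts the Protocol's Aim 1A, which asks whether "low-dose testosterone augmentation for 8 weeks leads to a significantly greater reduction in depressive symptoms than placebo". The documents do not support that. Those words give the duration of treatment, not a time point, and the SAP restates the aim as a comparison over an 8-week period. Its model matches its own endpoint, and averaging on-treatment scores is a legitimate choice. If the expected flat profile holds, averaging is also more powerful: where week 8 alone has 80% power, the average has 86% to 96% (assumed correlations of 0.8 down to 0.4).

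It can also be said that drop-out bias needs drift and unequal drop-out together; that the pilot had no drop-outs; that the largest shift shown requires a 9-point fall from week 2 to week 8; and that the SAP plans week-8 recovery, a missing-data sensitivity analysis and, under Aim 2, a test for differential drop-out. Most of this stands, and it limits the size of the problem. It does not remove it. The sensitivity analysis addresses the missing-at-random assumption rather than the mean structure, and the drop-out test describes an imbalance without correcting the estimate. Recovery helps in proportion to its success, which is unknown.

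**Conclusion.** The concern holds in a limited form. The listed model has no visit or arm-by-visit term, and the text leaves the visit main effect unclear. The weeks 2-8 average is unbiased with complete data. With drift and unequal drop-out, omitting visit shifts the arm estimate by about 0.2 to 0.6 MADRS points at 5% vs 25%, and by about half that at 10% vs 20%. Against a standard error of about 1.3, the largest shift is about half a standard error. The figures rest on assumed SDs, drift and drop-out, and they shrink towards zero as week-8 recovery approaches completeness.

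Separately, the plan has no means of checking the flat effect on which it relies, and no week-8 mean MADRS contrast. A reader might go further and conclude that dose titration dilutes the primary estimate. The documents do not establish this: titration runs both ways, the number of women affected is not given, and exposure is not response. Dilution relative to week 8 is conditional on an assumed building effect. The change below would reveal it but would not remove it from the primary average.

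**What to change.** In the SAP's Aim 1 Data Analysis, add visit (categorical: weeks 2, 4, 6, 8) and arm-by-visit as fixed effects. State that the primary contrast is the equally weighted weeks 2-8 average of the arm differences. Pre-specify the week-8 contrast from the same model as a supportive estimate. Make the same change for BFI and SF-36.

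The cost is SAP wording and six degrees of freedom (three for visit, three for arm-by-visit). No new data are needed. The week-8 contrast is less precise than the average, which is why the average stays primary.

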#### **RESEARCH DESIGN AND METHODS**

Briefly describe study design and anticipated enrollment, i.e., number of subjects to be enrolled by researchers study-wide and by Partners researchers. Provide a brief summary of the eligibility criteria (for example, age range, gender, medical condition). Include any local site restrictions, for example, "Enrollment at Partners will be limited to adults although the sponsor's protocol is open to both children and adults."

**Study Design:** After antidepressant therapy partial or nonresponse is established by documentation of failure to at least 8 weeks' treatment with an adequately dosed antidepressant therapy, A minimum of 100 subjects study-wide (60 from MGH) with MADRS $\geq$ 12 will enter the double-blind augmentation randomized-placebo-controlled treatment study. 50 of these subjects will be on active study drug and 50 will be control subjects on placebo. Eligible subjects will undergo baseline assessment of symptoms and biological measures and then be randomized to 1 of 2 groups: low-dose physiologic testosterone augmentation by transdermal preparation or placebo.

Antidepressant dose will be held steady during the trial. Outcome measures will examine the antidepressant efficacy of physiologic testosterone treatment (Aim 1), its tolerability (Aim 2) and its effects on 2 specific RDoC symptoms (Aim 3).

**Subject Enrollment:** A total of 330 women will be enrolled study-wide, of which 100 women with antidepressant-resistant MDD and 50 women with no psychiatric history will be eligible study-wide. Study subjects for the depressed population will be women, ages 21-75 with failure to remit following at least 8 weeks antidepressant trial documented by past treatment history.

In addition, 20 healthy controls without

depression will be recruited for the fMRI substudy healthy control population.

Up to 60 postmenopausal women who do not have current or past psychiatric disorders will also be screened to obtain 30 women who will be enrolled

as healthy controls.

Randomized Study Subject Population (n=60)

Inclusion Criteria for Randomized Study Subjects:

- 1. Female, age 21-75, who provide written informed consent
- 2. Free testosterone level no higher than the third quartile of the normal range
- 3. Meet DSM-IV criteria (by SCID) for current Major Depressive Disorder and have MADRS≥12

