
endpoint, we will determine the 8-week remission rate in an exploratory analysis. Remission will be defined as MADRS score<10. Comparison of ratios of remitters to the total number of study participants in the testosterone and placebo groups will be compared using a Fisher Exact test. Another secondary endpoint will be effects of testosterone on functional measures. The same methods as described for MADRS score analyses will be used to analyze functional measures, including the SF-36.

For Aim 1B, the primary analysis will be to determine whether the neuroactive metabolite of testosterone, 3a-diol, is an important determinant of the effects of testosterone on our primary endpoint, MADRS score. We expect to be able to distinguish the effect of 3a-diol from the effect of an increase in serum free testosterone levels because we expect the relative levels of the two hormones will differ, i.e. we expect that some study subjects will convert a greater proportion of testosterone to the 3α -diol metabolite than other study subjects. Analyzing the effect of both free testosterone and 3α-diol on the outcome (MADRS score) by linear regression, we hope to determine the relative importance of each hormone as a determinant of outcome. It is conceivable that both will correlate with the MADRS score, simply reflecting absorption of testosterone, and it is also possible that one will correlate with MADRS score, and the other will not. For instance, if the coefficient of the metabolite 3α -diol in a regression of outcome on 3α-diol and free testosterone is large while that of free testosterone is small, then we would conclude that the active factor is 3a-diol rather than free testosterone. If the correlation coefficient between the two of these is large, we would not have data to make a determination of which is active.

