Specific Aim 2: We will investigate in women with partial/nonresponse to antidepressant therapy whether adjunctive low-dose testosterone is safe and welltolerated in women with partial/nonresponse to antidepressant therapy. Experimental Strategy and Endpoints: To investigate whether adjunctive physiologic testosterone is safe and well-tolerated over the 8-week protocol, we will compare rates of adverse events in subjects randomized to testosterone augmentation to those receiving placebo using the SAFTEE-SI. These endpoints will also include increases in ALT and hirsutism and skin assessment scores and decreases in HDL cholesterol. The primary endpoint will be adverse effect rate.

• These data will determine whether adjunctive physiologic testosterone is safe and well-tolerated in women with relative partial/nonresponse to antidepressant therapy.

Data Analysis: Rates for each adverse effect will be computed by group. Differences between treatment groups in dropout rates will be examined using a Fisher's Exact test, though every effort will be made to retain subjects through the 8-week course. If a trend (p < .10) indicative of differential dropout is detected, a more detailed survival analysis will be completed to illustrate the timing and magnitude of these differences.

Specific Aim 3: Low-dose testosterone augmentation improves persistent/residual symptoms in women with antidepressant-resistant depression.

Experimental Strategy and Endpoints: To investigate the effects of low-dose testosterone augmentation on fatigue and energy in women with antidepressant-resistant depression, the 50 women with antidepressant-resistant depression

randomized to testosterone augmentation and 50 to the placebo arm of the 8-week randomized, double-blind placebo controlled study delineated in the "Overall Protocol", will be compared. Energy/fatigue and sexual function/libido endpoints will be measured at baseline and weeks 2, 4, 6 and 8. The primary endpoint will be BFI score weeks 2-8.

• These data will determine the effects of low-dose testosterone augmentation on fatigue and sexual function in women with antidepressant-resistant depression.

Data Analysis: The data will be analyzed using a mixed-effect linear regression model, using methods and assumptions as in Specific Aim 1 Data Analysis, above.

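### Low-priority efficiency gain: exploratory week-8 remission is compared by a valid but conservative Fisher test that leaves out baseline MADRS, which the SAP uses in its other efficacy models

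*SAP*

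**What the plan says.** In the SAP, Specific Aim 1, Data Analysis, remission is a secondary endpoint: "we will determine the 8-week remission rate in an exploratory analysis". The definition is an absolute cut-off: "Remission will be defined as MADRS score<10". The proportions of remitters "in the testosterone and placebo groups will be compared using a Fisher Exact test", with no covariate and no stratification factor.

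The same section treats the MADRS score differently: "The model will specify a baseline MADRS score and baseline non-responder vs. partial responder as covariates". That approach is then carried over to the functional endpoints ("The same methods as described for MADRS score analyses will be used to analyze functional measures, including the SF-36") and to Aim 3, fatigue and sexual function ("using methods and assumptions as in Specific Aim 1 Data Analysis, above"). Neither document plans an adjusted remission analysis.

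Entry is open-ended upwards. Item 3 of the protocol's inclusion criteria for randomised subjects reads "Meet DSM-IV criteria (by SCID) for current Major Depressive Disorder and have MADRS≥12", and no upper limit is given.

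**The concern.** Remission is a fixed score, so baseline decides how far a woman must fall to be counted. From 12 she needs 3 points to reach 9; from 30 she needs 21. If baseline predicts week 8 at all, part of the variation in remission is explained by a measurement already in hand, and the Fisher comparison does not use it. Among the between-arm efficacy comparisons whose method the SAP states, remission is the only one without a baseline covariate.

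A second, separate cost is that Fisher's test rejects less often than its nominal level when two arms of this size are compared.

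What is at stake is power and precision for one exploratory comparison.

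**Working it through.** **Inputs from the documents.** 50 women per arm; remission is MADRS below 10; entry at MADRS 12 or more; Fisher test without covariates. The plan gives no power or rate for remission, so there is no figure of its own to reproduce.

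**Inputs assumed.** Two-sided 5% (no level is stated). Baseline MADRS normal, SD 6, truncated at 12. Week-8 MADRS = slope × baseline + intercept − effect + N(0, SD 7), rounded. Effect 4 points on testosterone. Baseline mean/slope/intercept: 25/0.75/−2 (r 0.53), 22/0.5/2 (r 0.36) and 22/0.25/8 (r 0.19).

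**Step 1: true size of Fisher's test.** For a common remission rate p, size = Σ Bin(a; n1, p) × Bin(b; n2, p) over all tables (a, b) with Fisher p ≤ 0.05. At 50/50 this gives 1.8, 2.8, 3.1, 3.2 and 3.5% for p = 10, 20, 30, 40 and 50%. At 49/51 the same sum gives about 3-4.6%. The conservatism therefore depends strongly on exact balance.

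**Step 2: power with exactly 50 per arm.** The adjusted test fits logit P(remission) = β0 + β1 × baseline MADRS. It then takes U = Σ armᵢ(yᵢ − fittedᵢ) and refers U²/Var(U) to 3.84.

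| r | Remission, testosterone vs placebo | Fisher | Boschloo | Chi-square | Adjusted score |
|---|---|---|---|---|---|
| 0.53 | 34% vs 19% | 35.0% | 39.3% | 42.9% | 49.0% |
| 0.36 | 51% vs 31% | 47.9% | 54.3% | 56.3% | 58.9% |
| 0.19 | 49% vs 28% | 50.9% | 58.1% | 59.1% | 59.9% |

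**Step 3: split the gain.**
- Leaving Fisher (chi-square − Fisher): 42.9 − 35.0 = 7.9; 56.3 − 47.9 = 8.4; 59.1 − 50.9 = 8.2 points.
- Baseline MADRS (adjusted − chi-square): 49.0 − 42.9 = 6.1; 58.9 − 56.3 = 2.6; 59.9 − 59.1 = 0.8 points.
- Total: 14.0, 11.0 and 9.0 points.

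**Step 4: arms off by one.** Same model, 40,000 simulated trials per setting, Fisher → adjusted score, in the same order of r:
- 49 testosterone, 51 placebo: 38.9 → 49.8, 49.9 → 59.0, 53.0 → 60.4%. Gains are 10.9, 9.1 and 7.4 points, or about 7-11.
- 51 testosterone, 49 placebo: 38.7 → 49.3, 54.5 → 58.7, 57.0 → 59.7%. Gains are 10.6, 4.2 and 2.7 points.

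At 49/51, in either direction, Boschloo's test recovers only about 1-4 points over Fisher. At 50/50 it recovers about 4-7.

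**Step 5: error rate and precision of the alternative.** The adjusted score test has size about 5.1-5.4%. A re-randomisation p-value for the same statistic has size 4.9-5.0% and power 48.2, 58.1 and 58.7%, about 1 point less than the asymptotic version. The 95% CI for the standardised risk difference is 31.1 against 33.5 percentage points wide (7% narrower), 36.2 against 37.3 (3%) and 36.9 against 36.9 (0%).

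**The case against.** The strongest reply is that this is a preference. Fisher's test is valid, the endpoint is labelled exploratory, the efficacy conclusion rests on a model that already adjusts for baseline, and an unadjusted comparison of two proportions is easy to read. All of that stands, and it is why the priority is low.

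The size of the loss is also open to challenge, with good reason. The largest component comes from Fisher's conservatism at exactly 50/50. The protocol speaks of a minimum of 100 women, and the SAP says "The randomization will be stratified by site, estrogen use, and one vs. more than one adequate antidepressant therapy trial" without giving a block scheme, so arms of slightly different size are likely. One woman's difference removes a good part of the cost (step 4).

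Part of the gain is also bought with a looser error rate. Holding both tests to a 5% ceiling, the fair comparison at 50/50 is re-randomised score against Boschloo: 48.2 − 39.3 = 8.9, 58.1 − 54.3 = 3.8 and 58.7 − 58.1 = 0.6 points.

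Stronger readings are tempting and are not supported. A reader might infer that the remission test is wrong, or that a chance baseline imbalance would bias it. Randomisation makes such imbalance part of the error that Fisher's test already allows for; it costs precision only. Nor do the documents show that baseline MADRS is the main source of the gain. They give no correlation, and over r of 0.2 to 0.5 with 50 per arm the covariate adds less than leaving Fisher does.

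**Conclusion.** The point holds as a cheap, optional improvement. Fisher's test is a valid choice here, but it gives up some power and leaves out a covariate that the SAP uses for its other efficacy outcomes.

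On the assumed inputs, the adjusted analysis gains about 9-14 points with exactly 50 per arm. With arms one woman apart the gain is about 7-11 points if testosterone is the smaller arm, and it can be as little as about 3 if testosterone is the larger. Baseline MADRS itself accounts for about 1-6 points at 50/50, and about 1 or less if r is near 0.2. Boschloo's test is not a substitute, because its advantage over Fisher shrinks to about 1-4 points once the arms differ slightly.

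That Fisher is conservative follows from exact enumeration and needs only the arm sizes and the 5% level. Every power figure depends on remission rates, a baseline spread, an effect and a correlation that the documents do not give. The primary MADRS conclusion does not change.

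**What to change.** In the SAP's remission paragraph, make the main comparison a logistic regression of week-8 remission on arm and baseline MADRS, with a score test for arm. Report the standardised risk difference with its 95% CI, so that the result stays on the scale of proportions. Keep Fisher's test as the supportive check, on the same women and with the same handling of a missing week-8 score.

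The cost is about one SAP sentence and a two-term model on data already collected; no trial procedure changes. The downside is the loss of Fisher's guaranteed 5% ceiling. If that ceiling matters, take the p-value by re-randomising the same statistic within the randomisation strata, at about 1 point of power. If baseline proves a weak predictor, little is gained from the covariate.
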